## Amended Statistical Analysis Plan

The CSP Amendment 4 included changes to patient inclusion and exclusion criteria and to prohibited/ restricted concomitant therapy. Data collection and reporting specifications were updated for worsening of depression, medication error or potential overdose and events of clinical significance. Changes between CSP Amendment 3 to 4 with specific impact in data presentation were

- Section 9.2.7.8 abnormal hematology, biochemistry or urinalysis results may be repeated at the investigator's discretion to rule out laboratory error, or to confirm patient eligibility or safety.
- Section 10.5.2.1 on the primary endpoint (change in MADRS score), as assessed at Week 6, a statistically significant GROUP\*TIME interaction effect, with greater reductions in MADRS scores in the TS-121 groups, will be interpreted as indicating efficacy (GROUP: Placebo, TS-121 10 mg and TS-121 50 mg, TIME: Week 2, Week 4 and Week 6)

# Statistical Analysis Plan

Taisho Pharmaceutical R&D Inc.  
Protocol TS121-US201

Final 2.0  
18 Dec 2018

Statistical Analysis Plan (SAP)

CONFIDENTIAL

- Section 11.3 Event of Clinical Significance (EOCS): Suicidal ideation and behavior, and lens opacity are considered as EOCS
- Sections 8.5 and 11.4 Patients with a CGI-I score of 6 or 7 at any time during the study will also be evaluated for possible discontinuation from the study. In the case of CGI-I scores of 6 or 7, the investigator will write a note justifying either discontinuation or continuation of the participant in the study. A CGI-I score of 6 or 7 at any time during the study should be considered as an AE of worsening of depression.

The amended SAP addresses missing data of two types: missing item responses for a given rating scale for calculation of the scale's total scores and missing visits data in the mixed model repeated measures analysis (MMRM). The amended SAP also describes presentation of local laboratory hematology data.

## 1. OVERVIEW OF THE STUDY

This multicenter study is comprised of a screening period of up to 4 weeks, with a 2-week single-blind placebo lead-in period followed by a 6-week randomized, double-blind, placebo-controlled treatment period with a 2-week follow-up period. The objectives are to compare the safety, efficacy, pharmacokinetics, and exploratory pharmacodynamics of TS-121 (drug substance code [REDACTED]) to placebo as an adjunctive treatment for patients with major depressive disorder (MDD) (Figure 1). Patients must remain on the same single antidepressant, selective serotonin reuptake inhibitor (SSRI), serotonin norepinephrine reuptake inhibitor (SNRI), or bupropion for 6 weeks, with a fixed dose for 4 weeks prior to screening. Patients will remain on this fixed dose of their current antidepressant therapy (ADT) throughout the course of the study.

Visit 1 (Screening): Patients will visit the site for screening assessments and an initial review of study requirements. In addition to confirming the diagnosis of MDD by MINI, a trained site rater will employ the 17-items Hamilton depression scale (HAM-D), which will be subsequently confirmed through an additional HAM-D assessment conducted by a central rater (Visit 1.1) prior to a 2-week placebo lead-in period.

Visit 1.1 (Screening): The central rater will contact the patient as scheduled, and will administer the Massachusetts General Hospital Antidepressant Treatment Response Questionnaire (MGH-ATRQ) for assessment of current ADT, adequacy of duration and dose of prior and current ADT, as well as degree of improvement. The central rater will also complete the HAM-D

# Statistical Analysis Plan

Taisho Pharmaceutical R&D Inc.  
Protocol TS121-US201

Final 2.0  
18 Dec 2018  
CONFIDENTIAL

Statistical Analysis Plan (SAP)

assessment and inventory of symptoms: State versus Trait; Assessability; Face validity; Ecological validity; and Rule of three Ps (pervasive, persistent, and pathological) (SAFER) for confirmation of placebo lead-in eligibility. Results will be communicated to the site prior to Visit 2.

Visit 2 (Start of Placebo Lead-In): Following initial eligibility confirmation, qualified patients will return to the site initiating a 2-week, single-blind placebo lead-in period. An ophthalmologist will conduct a thorough eye examination (including slit lamp under mydriasis). Patients will schedule another phone call for central rater assessments (Visit 2.1), and Visit 3 will be scheduled.

Visit 2.1 (End of Placebo Lead-In): Response to placebo will be assessed using HAM-D by a central rater. The current HAM-D score and change in HAM-D score from Visit 1.1 to Visit 2.1 will be used to determine eligibility.

Visit 3 (Baseline): After completing the placebo lead-in period, patients will return to the site for baseline evaluations. Following confirmation of eligibility, patients will be randomly assigned to receive TS-121 10 mg, 50 mg, or placebo in a 1:1:1 ratio. Patients will be instructed to continue taking investigational product once-daily in the morning and to maintain their current ADT.

Visits 4 (Week 2) and 5 (Week 4): Patients will return to the site for safety and efficacy assessments, dosing compliance, drug accountability and dispensing of a new supply of investigational product. Compliance with the dosing schedule will be assessed. Visit 5 and Visit 6 will be scheduled.

Visit 6 (Week 6): Patients will return to the site for end-of-treatment safety (including ophthalmological examination), efficacy, pharmacokinetic, and exploratory pharmacodynamic assessments and final drug accountability.

End of Treatment (EOT): The EOT visit is Visit 6 for patients who complete treatment and is the last assessment closest to the last treatment day for patients who discontinued from treatment early or failed to complete Visit 6.

Visit 7 (Follow-up): Patients will return to the site for a follow-up evaluation of safety (including ophthalmological examination) and efficacy assessments approximately two weeks after Visit 6.

ET Follow-up: The visit completed approximately 14 days after the patient's last dose for patients who discontinued from treatment early.

# Statistical Analysis Plan

Taisho Pharmaceutical R&D Inc.  
Protocol TS121-US201

Final 2.0  
18 Dec 2018  
CONFIDENTIAL

Statistical Analysis Plan (SAP)

[figure not shown]

Figure 1. Study Design

## 2. STUDY OBJECTIVES AND ENDPOINTS

### 2.1 Primary Objectives

- To evaluate the safety and tolerability of TS-121 compared to placebo in MDD patients
- To evaluate the efficacy of two dose levels of TS-121 compared to placebo on MDD symptoms in MDD patients

### 2.2 Exploratory Objective

- To evaluate the effectiveness of biomarkers in predicting TS-121 response with retrospective stratification of patients via baseline values of HPA axis and inflammatory biomarkers

### 2.3 Primary Efficacy Endpoint

- Change in MADRS total score from Visit 3 (Baseline assessment) to Week 6/EOT

### 2.4 Secondary Efficacy Endpoint

- Change from Visit 3 to Week 6/EOT for CGI-S, SDQ, and HAM-A total scores

# Statistical Analysis Plan

Taisho Pharmaceutical R&D Inc.  
Protocol TS121-US201

Final 2.0  
18 Dec 2018  
CONFIDENTIAL

Statistical Analysis Plan (SAP)

- Percentage of CGI-I improvers (“Very much improved” or “Much improved”)
- Percentage of MADRS responders ( $\geq 50\%$  reduction in total score)

## 2.5 Exploratory Endpoint

- Pharmacokinetic data from Visit 6 may be explored relative to study results (mental health assessments and/or laboratory values)
- Change from Visit 3 to Visit 6 for plasma copeptin and inflammatory markers (TNF- $\alpha$ , IL-1, IL-6, HS-CRP)
- To evaluate the effectiveness of biomarkers in predicting TS-121 response with retrospective stratification of patients via baseline values of HPA axis and inflammatory biomarkers consisting of:
  - Hair cortisol
  - Salivary cortisol
  - Urine cortisol
  - Plasma copeptin, and
  - Inflammatory markers (TNF- $\alpha$ , IL-1, IL-6, HS-CRP)

## 3. STUDY DESIGN

### 3.1 Study Procedures and Observations

Refer to Table 1.

**Table 1 Study Procedures and Observations**

Procedures	Visit 1**** (Screening) Day -28 to Day -7	Visit 1.1**** (Screening) Day -13 to Day -2	Visit 2 (Start of Placebo Lead-in) Day 1	Visit 2.1 (End of Placebo Lead-in) Day 13 (±2)	Screen* failure ONLY End of Study	Visit 3** (Baseline) Day 15 (+3)	Visit 4 (Week 2) Day 29 (±3)	Visit 5 (Week 4) Day 43 (±3)	Visit 6 (Week 6) Day 57 (±3)	Visit 7 (Follow-up) Day 71 (±3)	ET***	
											ET	Follo Up
Site Visit	X		X		X	X	X	X	X	X	X	X
Informed Consent (Study, PGx, HIPAA) a	X											
Demography	X											
Inclusion and Exclusion Criteria	X		X			X						
Evaluation of Medical and Psychiatric History	X		X									
Evaluation of Prior Medication History	X											
Serology Screen	X											
Urine Drug Screen	X					X						
Urine Pregnancy (all females)	X		X			X	X	X	X	X	X	X
Height	X											
Body Weight	X		X			X	X	X	X	X	X	X
Body Mass Index (BMI)	X											
Physical and Neurological Examination	X				X	X		X	X	X	X	X
Ophthalmological Examinations b			X					X	X	X	X	X
Columbia Suicide Severity Rating Scale (C-SSRS)	X				X	X	X	X	X	X	X	X
MINI	X											
HAM-D (SITE Rater)	X											
MGH ATRQ (Central Rater)		X										
HAM-D (Central Rater)		X		X								
SAFER Inventory (Central Rater)		X										
MADRS c						X	X	X	X	X		

**Table 1 Study Procedures and Observations**

Procedures	Visit 1**** (Screening) Day -28 to Day -7	Visit 1.1**** (Screening) Day -13 to Day -2	Visit 2 (Start of Placebo Lead-in) Day 1	Visit 2.1 (End of Placebo Lead-in) Day 13 (±2)	Screen* failure ONLY End of Study	Visit 3** (Baseline) Day 15 (+3)	Visit 4 (Week 2) Day 29 (±3)	Visit 5 (Week 4) Day 43 (±3)	Visit 6 (Week 6) Day 57 (±3)	Visit 7 (Follow-up) Day 71 (±3)	ET***	
											ET	Follow Up
MADRS Central Rater Oversight						X ←				→ X		
CGI-S						X	X	X	X	X		
CGI-I							X	X	X	X		
HAM-A						X	X	X	X	X		
SDQ						X	X	X	X	X		
Vital Signs (seated)	X		X			X	X	X	X	X	X	X
12-Lead Electrocardiogram (ECG)	X					X	X	X	X	X	X	X
Clinical Laboratory Tests	X					X	X	X	X	X	X	X
Exploratory Safety Assessments			X			X	X	X	X	X	X	X
Hair Cortisol Level						X						
Plasma Copeptin Level						X			X			
Salivary Cortisol Level (at home) d			Dispense Kit			X						
Urine Cortisol Level (pooled for 8 hr at home) d			Dispense Kit			X						
Inflammatory Markers (TNF-α, IL-1, IL-6, HS-CRP)						X			X			
Pharmacokinetic Blood Sampling ([REDACTED])									X			
Pharmacogenomic Blood Sampling						X						
Placebo administration under single-blind			X ←			→ X						
Randomization						X						
Investigational product dispensing, accountability and compliance check e			X			X	X	X	X			
Dose administration under double-blind						X ←				→ X		
Drug adherence (AiCure) f			X ←							→ X		
Adverse Event Inquiry & Reporting			X ←							→ X	X	X

**Table 1 Study Procedures and Observations**

Procedures	Visit 1**** (Screening) Day -28 to Day -7	Visit 1.1**** (Screening) Day -13 to Day -2	Visit 2 (Start of Placebo Lead-in) Day 1	Visit 2.1 (End of Placebo Lead-in) Day 13 (±2)	Screen* failure ONLY End of Study	Visit 3** (Baseline) Day 15 (+3)	Visit 4 (Week 2) Day 29 (±3)	Visit 5 (Week 4) Day 43 (±3)	Visit 6 (Week 6) Day 57 (±3)	Visit 7 (Follow-up) Day 71 (±3)	ET***	
											ET	Follow Up
Concomitant Medication Inquiry & Reporting	X	←								→ X	X	X

- \* End of Study (Screen failure only): Patients who discontinue between Visits 2 and 3 only will undergo the procedures specified above.
  - \*\* Visit 3 must be performed after obtaining results for Visit 2.1.
  - \*\*\* The Early Termination (ET) visit should be performed as early as possible after discontinuation. ET follow-up visit will also be necessary approximately 14 days after the patient’s last dose.
  - \*\*\*\* Visit 1 must be performed prior to Visit 1.1.
- a Informed consent for PGx must be obtained prior to blood collection at Visit 3.
  - b Ophthalmological Examination: Must be conducted by an ophthalmologist. Examination can be performed within -5 days of study Day 1 (Day -5 to Day 1) as Visit 2 assessment.
  - c MADRS should be conducted prior to any other mental health assessments and safety/PK/PD assessments.
  - d Urinary and Salivary Cortisol: Dispense kits at Visit 2.
  - e Investigational product dispensing, accountability and compliance checks: Accountability and compliance checks will be performed at Visits 3 to 6. Administration of the investigational product for the placebo lead-in period will start on the morning following Visit 2 (study Day 2). Administration of the investigational product for the treatment period will start on the morning following Visit 3 (study Day 16).
  - f Drug Adherence: Daily dosing by patients of current ADT and investigational product (TS-121 or placebo) will be monitored using AiCure technology on the patient’s smart phone or a device provisioned by the site (See CSP Section 8.1.3, Treatment Compliance).

# Statistical Analysis Plan

Taisho Pharmaceutical R&D Inc.  
Protocol TS121-US201

Statistical Analysis Plan (SAP)

Final 2.0  
18 Dec 2018  
CONFIDENTIAL

## 4. STUDY POPULATION

It is estimated that the study will screen approximately 300 patients in order to randomize approximately 180 MDD patients.

Patients withdrawn for safety or tolerability will not be replaced. Patients discontinued due to other reasons, e.g., dosing compliance, may be replaced at the discretion of the sponsor in order to achieve the study objectives.

## 5. STATISTICAL BASIS FOR SAMPLE SIZE

The total number of patients enrolled in the study is based on practical consideration and not on statistical power calculations. These sample sizes are considered adequate to meet the study objectives, based on clinical considerations and other MDD trials, and will allow trends to be detected with regards to efficacy and PD effects of TS-121 in this patient population.

## 6. STATISTICAL ANALYSIS CONVENTIONS

### 6.1 Analysis Variables, Criteria for Evaluation

#### 6.1.1 Demographic and Background Variables

The following patient history, demographic and anthropometric information will be recorded:

- Date of informed consent
- Age calculated as (date of informed consent – date of birth)/365.25. Date of birth will be collected using interactive response technology (IRT) of the IWRS.
- Gender
- Ethnicity
- Race
- Height and weight
- BMI

# Statistical Analysis Plan

Taisho Pharmaceutical R&D Inc.  
Protocol TS121-US201

Statistical Analysis Plan (SAP)

Final 2.0  
18 Dec 2018  
CONFIDENTIAL

- Medical and/or psychiatric history (within the past 3 years)

New or existing medical or psychiatric conditions reported prior to first administration of the investigational product [from the placebo lead-in period ] will be captured as medical history, whereas any new, untoward, or worsening medical or psychiatric conditions reported after first administration of the investigational product during the placebo lead-in period will be captured as adverse events.

- Concomitant medications

All medications used during the study will be recorded. Prior ADTs other than a current SSRI/SNRI/bupropion and prohibited medications that might influence HPA axis function used within 3 months of Visit 1 will also be recorded.

- Screening laboratory test results will be recorded

- **Serology:** Hepatitis B surface antigen (HBsAg), HIV screening and serum antibodies against Hepatitis C virus (anti-HCV antibody)
- **Urine drug screen:** The following controlled substances will be tested at Visit 1 and at Visit 3: amphetamine, barbiturates, benzodiazepines, cocaine, methadone, morphine/opiates, methamphetamine, marijuana (THC), phencyclidine (PCP), and ecstasy (MDMA).
- **Pregnancy:** For all female participants, urine pregnancy samples will be tested at specified visits indicated in the Schedule of Procedures, Table 1.

All medical history will be coded using Version 19.1 of the Medical Dictionary for Regulatory Activities (MedDRA).

Concomitant medications will be coded using the World Health Organization Drug Dictionary Enhanced (WHODDE September 2016).

## 6.1.2 Screening Mental Health Assessments

### ***6.1.2.1 MINI-International Neuropsychiatric Interview (MINI)***

Results of the MINI (Version 7.0.2) administered at Visit 1 will be recorded in the patient's source records only.

# Statistical Analysis Plan

Taisho Pharmaceutical R&D Inc.  
Protocol TS121-US201

Statistical Analysis Plan (SAP)

Final 2.0  
18 Dec 2018  
CONFIDENTIAL

## **6.1.2.2 17 items Hamilton Rating Scale (HAM-D)**

Results of the HAM-D (October 2010 for the DUAG-8 project) conducted by the trained site rater at Visit 1 and of the remote HAM-D conducted by central raters at Visit 1.1 and Visit 2.1 will be captured.

## **6.1.2.3 SAFER Interview**

The interview conducted at Visit 1.1 includes the SAFER inventory of symptoms, the HAM-D and the MGH-ATRQ. Previous and current ADT information collected using the MGH-ATRQ will be recorded with prior and concomitant medications. Start date of MDD current episode will be recorded.

## **6.1.3 Safety Variables**

Safety and tolerability will be assessed from the time the patient is administered the investigational product during the placebo lead-in period through the final study procedure as specified in the Schedule of Procedures, Table 1.

Safety measures include:

- Adverse events
- Clinical laboratory tests (hematology, biochemistry and urinalysis)
- Vital signs
- 12-Lead ECG
- Body weight
- Routine physical examination
- Comprehensive neurological examination
- Ophthalmological examination
- Columbia Suicide Severity Rating Scales (C-SSRS)
- Exploratory Safety Assessments

# Statistical Analysis Plan

Taisho Pharmaceutical R&D Inc.  
Protocol TS121-US201

Statistical Analysis Plan (SAP)

Final 2.0  
18 Dec 2018  
CONFIDENTIAL

## **6.1.3.1 Adverse Events**

An adverse event (AE) is defined as any untoward medical occurrence in a patient administered an investigational product, and which does not necessarily have a causal relationship to investigational product. An AE can be any unfavorable or unintended sign (including an abnormal finding), symptom, or disease. AEs include any occurrence that is new in onset or aggravated in severity or frequency from the baseline condition, or abnormal results of diagnostic procedures (including clinically significant laboratory test abnormalities). AEs also include an intentional or accidental overdose, whether or not it is associated with symptoms. An overdose is defined as ingestion of the investigational product (accidental or intentional) more than 3 capsules in the same calendar day.

AEs will be recorded after the first administration of the investigational product in the placebo lead-in period through follow-up. AEs with onset date and time (if available) after the first administration of randomized treatment will be considered treatment emergent AE (TEAE).

Any AEs with incomplete start and end dates/times will be treated as follows:

- Adverse events with unknown start and/or end times (but where the date is known) will be imputed as post-dose for events on first treatment day of placebo lead-in or randomized treatment or with a time of 00:00 for other days. The missing time will be shown blank in the listings.
- Adverse events with incomplete start day and known month will be imputed as the later of: day of first placebo lead-in dose or first randomized dose started in that month or first of the month. Missing day will be printed -- in the listings.
- Adverse events with incomplete start dates missing month and day will be considered as the later of: day of first placebo lead-in dose or first randomized dose started in that year or January 1. Missing month and day will be printed ----- in the listings.
- Adverse events with completely unknown start dates will be considered as treatment emergent for the tabulations and the missing dates will be shown as ----- in the listings.

Details of AE classification for severity (mild, moderate or severe), action taken and relationship to test drug (not related, possibly related, probably related and definitely related) are provided in Appendix C. All AEs will be coded using MedDRA Version 19.1.

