## **6.3.16.1 Adverse Events**

The following AE listings will be produced:

- All AEs [Listing 16.2.7.1]
- SAEs [Listing 16.2.7.2]
- AEs leading to Study Drug Discontinuation [Listing 16.2.7.3]
- EOCSs [Listing 16.2.7.4]
- Overdose [Listing 16.2.7.5]

The following information will be included in AE listings: Subject number, age, sex and race, treatment group, verbatim term, MedDRA preferred term (PT), system organ class (SOC), SAE indicator flag, AE onset date (and time) and study day, AE end date (and time), duration (days), severity, relationship to study drug, action taken for study drug, action taken to treat, AE outcome, and treatment emergent (TEAE) flag. Adverse events with onset date on or later than date of first dose of the randomized treatment, which also meet one of the following two criteria, will be considered TEAE.

- The AE was not present prior to the first dose of study drug for the treatment period
- The AE was present prior to the first dose of study drug for the treatment period and increased in severity

Each summary tabulation of AEs will include the number and percentage of patients who experienced TEAEs grouped to treatment (TS-121 10 mg, TS-121 50 mg and placebo) and the number and percentage of all patients who experienced AEs during placebo lead-in.

The overview of AEs includes the number and percentage of patients with at least one AE, with any SAE or with an AE that led to study discontinuation [Table 14.3.1.1].

Tables of number (and percentage) of patients with AEs summarized by SOC, PT and maximum severity [Table 14.3.1.2] and by SOC, PT and relationship to investigational product [Table 14.3.1.3] will be presented by treatment group for the safety analysis population. Treatment related AEs include those that are marked as “possibly”, “probably” or “definitely related to

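### The SAP's rules for incomplete AE start dates never check the end date, so a lead-in AE known to have ended can be dated to the first randomized dose, and the two TEAE definitions then disagree about it

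*SAP*

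**What the plan says.** AEs are recorded from the first lead-in placebo dose (SAP 6.1.3.1), so lead-in events are in the data to which the date rules apply. The rules for incomplete starts in that section are:

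- Day missing, month known: the start is "imputed as the later of: day of first placebo lead-in dose or first randomized dose started in that month or first of the month".
- Month and day missing: the start is "considered as the later of: day of first placebo lead-in dose or first randomized dose started in that year or January 1".
- Nothing known: "Adverse events with completely unknown start dates will be considered as treatment emergent for the tabulations".
- Time missing: it "will be imputed as post-dose for events on first treatment day of placebo lead-in or randomized treatment".

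SAP 6.3.4 (Missing Data) adds no further rule and refers back to 6.1.3.1.

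The SAP defines a TEAE twice. In 6.1.3.1 the test is onset alone: "AEs with onset date and time (if available) after the first administration of randomized treatment will be considered treatment emergent AE (TEAE". In 6.3.16.1, which governs the AE listings and tables, a TEAE is an event with "onset date on or later than date of first dose of the randomized treatment, which also meet one of the following two criteria". The two criteria are "The AE was not present prior to the first dose of study drug for the treatment period" and "The AE was present prior to the first dose of study drug for the treatment period and increased in severity".

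**The concern.** When the timing of an event is unknown, leaning towards treatment-emergent is ordinary caution. A recorded end date before the first randomized dose removes the doubt, because the event cannot have started on or after that dose. The rules discard this information and can give an event a start later than its own end.

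Safety and tolerability is a primary objective. SAP 6.3.16.1 tabulates TEAEs by arm and reports lead-in AEs separately. An event moved in this way leaves the lead-in column, where it belongs, and enters an arm's column, where the data show it does not. With 60 patients planned per arm, one affected patient adds up to 1/60 = 1.7 percentage points to an arm's TEAE incidence.

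**Working it through.** The documents give no figure on this point, so there is none to reproduce.

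**Inputs.** The first lead-in dose is on Day 2 and the first randomized dose on Day 16 (SAP Table 1, note e). Visit 3 has a +3 day window (Protocol 9.3), so the first randomized dose can be as late as Day 19. The lead-in then spans 14 to 17 dosing days.

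**The rule as a formula.** Imputed start = the latest of (a) the 1st of the start month, (b) the first lead-in dose if it falls in that month, and (c) the first randomized dose if it falls in that month. The end date does not enter.

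**Case 1, same month.** Lead-in dose 2 March, randomized dose 16 March, AE start in March with the day missing, AE end 8 March. Imputed start = max(1 March, 2 March, 16 March) = 16 March, which is 8 days after the event ended.

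- Under 6.1.3.1 the event is a TEAE, taking an unknown time on that day as post-dose. The time rule is worded for events whose date is known. I assume it also applies once the date has been imputed.
- Under 6.3.16.1 it passes the date test. If presence before the dose is judged from the imputed start, it also passes the first criterion and is a TEAE. If presence is judged from the recorded end, the event was present earlier and fails that criterion. Unless it worsened, it is then not a TEAE. The SAP does not say which reading applies.

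**Case 2, lead-in across two months.** Lead-in dose 25 March, randomized dose 8 April. A March start is imputed to 25 March and stays in the lead-in. Only an April start moves to 8 April.

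**How often the move occurs.** If the first randomized dose is on day d of a 30-day month and the lead-in has n = 14 days, then k = min(14, d − 1) lead-in days share its month.

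- All lead-in onset days: the mean of k/14 over d = 1 to 30 is (105 + 15 × 14)/(30 × 14) = 315/420 = 75%.
- AEs that ended before the dose, with every onset and end pair inside the lead-in equally likely: there are 14 × 15/2 = 105 pairs, of which k(k + 1)/2 are moved. The mean share is (560 + 15 × 105)/(30 × 105) = 2135/3150 = 68%.

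Applying the rule to each of 365 consecutive Visit 2 dates, with real month lengths, gives:

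| First randomized dose | Lead-in days | All lead-in onset days moved, day missing | Ended before the dose and moved, day missing | All lead-in onset days moved, month and day missing |
|---|---|---|---|---|
| Day 16 | 14 | 75.3% | 68.2% | 97.9% |
| Day 17 | 15 | 73.7% | 66.0% | 97.8% |
| Day 18 | 16 | 72.1% | 63.8% | 97.7% |
| Day 19 | 17 | 70.4% | 61.6% | 97.5% |

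The fourth column answers this point, since only events that ended before the dose are provably misdated.

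**With an end-date check.** If candidate dates later than the known end are dropped, the start in Case 1 becomes 2 March, and the share in the fourth column falls to 0%.

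**The case against.** The strongest reply is that 6.3.16.1 governs the tables and already has the needed condition. An AE that stopped during the lead-in was present before the first randomized dose, so on the plain words it is not a TEAE unless it worsened. This stands as a reading, and it rules out the inference that every such event will be miscounted. It does not close the gap. The SAP does not say whether presence is judged from imputed or recorded dates, and 6.1.3.1 defines the same term without the condition. The rule for wholly unknown starts assigns the event to the tabulations outright, with no exception for an end date in the lead-in.

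A reader might also infer more than the documents support in four ways:

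- That any lead-in AE with a missing start day is moved. Case 2 shows otherwise. Patients who fail during the lead-in are in the safety population but have no randomized dose, so the partial-date rules cannot move their events.
- That three quarters of such AEs are misclassified. That share covers all lead-in onset days, including events still ongoing at the first randomized dose.
- That the listings will show false starts or negative durations. Missing days are printed as dashes, and the SAP does not say that duration is computed from imputed dates.
- That the rule biases the comparison between arms. It is identical in all three, and nothing in the documents points to a differential effect.

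The practical effect may also be nil. Protocol 11.1.2 asks for start and stop dates, AE inquiry runs from Visit 2, and Visit 3 precedes the first randomized dose. An event with a complete end date but no start day should be uncommon in so short a period.

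**Conclusion.** The point holds as a minor error in the rules as written. For a randomized patient whose first randomized dose falls in the AE's known start month (or year, if the month is missing), the imputation can place the start after a recorded end. That event is a TEAE under 6.1.3.1. Under 6.3.16.1 its status depends on an unstated programming choice. A wholly undated start is treatment-emergent regardless of its end date.

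If the start day were missing, about 62% to 68% of lead-in AEs that ended before the first randomized dose would be moved. This assumes evenly spread visit and onset dates and equally likely onset and end pairs. The effect on the tables cannot be sized, because the documents give no count of incomplete dates; I expect it to be very small. Its direction is a higher TEAE incidence and a lower lead-in count in all arms alike.

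**What to change.** Add to SAP 6.1.3.1: an imputed start date may not be later than a known AE end date (use the latest candidate date on or before that end), and an AE whose known end date is before the first randomized dose is not a TEAE, whether its start is partial or wholly missing. Where the end date is itself incomplete, the present rule can stand.

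Use one TEAE definition in 6.1.3.1 and 6.3.16.1, and state that presence before the first randomized dose is judged from recorded dates wherever these settle it.

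The cost is one sentence for the end-date check, one line of code, and a short edit to align the definitions. No new data are needed, and caution is kept for events whose timing really is unknown. The change belongs before database lock. If made later, it should be reported as an SAP revision with its reason, as the SAP already requires.
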